5.3.3. PD Endpoints

Analysis of PD endpoints using mixed model repeated measures (MMRM) makes the assumption that the data are "missing at random (MAR)" and utilizes all relevant partial data obtained from a subject without requiring a specific imputation of missing values.

5.3.4. Efficacy Endpoint

Missing data will not be imputed.

6. ANALYSES AND SUMMARIES

6.1. Primary Safety Endpoint(s)

A set of summary tables split by dose level and cohort will be produced to evaluate any potential risk associated with the safety and toleration of administering PF-06741086. In addition, if data permits, summary tables will also be presented for hemophilia A and hemophilia B subjects separately. Diagnosis of hemophilia A or B will be derived based on Factor VIII activity or Factor IX activity level ($\leq 1\%$) respectively at screening.

No formal analyses are planned for safety data. The safety and other endpoints detailed in Section 3.1 will be listed and summarized in accordance with sponsor reporting standards, where the resulting data presentations will consist of subjects from the Safety Analysis Set (as defined in Section 4.2). The details are provided in Section 6.4.6.

6.2. Secondary Endpoint(s)

6.2.1. Efficacy Endpoint

6.2.1.1. Statistical Analysis

The efficacy analysis will be conducted in the PPAS. A historical On Demand group will be constructed using the following internal Pfizer studies: ReFacto AF 3082B2-4432 (B1831004), BeneFIX B1821010, and BeneFIX 3090A1-400 (B1821004). Subjects who are on On Demand treatment in B1831004, as well as data from the On Demand period in B1821004 and B1821010 will be used to construct the historical On Demand group. The resulting dataset will be further filtered to match the key inclusion/exclusion criteria of B7841002 based on age and factor activity ($18 \leq \text{age} \leq 65$ and factor activity $\leq 1\%$). Outliers with extremely high ABR will be removed from the pooled On Demand group, if appropriate. All resulting subjects will be included in the historical control group.

The frequency of bleedings will be analyzed using a negative binomial model as detailed in Section 5.2.3. The ratio of ABR and its 80% 2-sided CI in the PF-06741086 arm versus that in the historical On Demand group will be generated for each dose cohort. The corresponding p-value will also be presented. Model based ABR and its 80%CI will be generated for each dose cohort.

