### 5.7.1. Prohibited Medications

Factor VIII (within 72 hours) or Factor IX replacement therapy (within 96 hours), or bypass agent therapy (FVIIa or APCC: within 72 hours), before Screening is prohibited. Depending on the coagulation factor product in use, additional wash out time may be required prior to the screening assessments to achieve a factor activity level  $\leq 1\%$ . If a subject experiences an acute bleeding episode during this washout period requiring treatment with a Factor VIII or IX replacement therapy, or bypass agent therapy, the subject is to be stabilized utilizing this regimen and a new washout period should be initiated. The regimen used to treat the episode should be recorded as a prior medication.

Factor VIII (within 72 hours) or Factor IX replacement therapy (within 96 hours), or bypass agent therapy (for FVIIa or APCC: at least 72 hours), before Day 1 treatment is also prohibited. If a subject experiences an acute bleeding episode during this washout period requiring treatment with a Factor VIII or IX replacement therapy, or bypass agent therapy, the subject is to be stabilized utilizing this regimen and a new washout period should be initiated. The regimen used to treat the episode should be recorded as a concomitant medication. All acute bleeding episodes between Screening and Day 1 must be recorded.

Treatment with rFVIIa **at a dose level greater than approximately 90  $\mu\text{g}/\text{kg}$  is prohibited throughout the study**. If a subject receiving investigational product is subsequently administered a rFVIIa dose greater than approximately 90  $\mu\text{g}/\text{kg}$ , the investigator must immediately contact the Sponsor's medical monitor to discuss the case to determine if the respective subject should continue to receive IP, remain in the study, or be withdrawn immediately.

**Treatment with APCC (eg, FEIBA) is prohibited throughout the study.** Subjects receiving such therapy, who cannot substitute treatment with rFVIIa, at the 90  $\mu\text{g}/\text{kg}$  per dose are not to be enrolled into this study. Subjects who are treated with investigational product who are subsequently administered APCC therapy must be withdrawn from treatment with investigational product immediately. These subjects should be followed at all remaining clinic visits up to Day 113 to monitor for adverse events and any additional safety concerns.

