### 5.7.2. Treatment(s) for Acute Bleeding Episodes

If a subject experiences an acute bleeding episode at any point throughout the study, the subject is to be stabilized utilizing the subject's standard hemostatic treatment regimen

(which may include Factor VIII or Factor IX replacement therapy, or rFVIIa bypass agent therapy at approximately 90 µg/kg per dose). Pausing or withdrawal of treatment with investigational product is not required in the event of a breakthrough bleed, but may be considered at the discretion of the investigator. See [Section 7.2.5](#) for additional information.

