## 7.2. Efficacy

### 7.2.1. Hemophilic Bleeding Episodes

During this study, the investigator (or qualified designee) will review the subject diary with the subject, and inquire about and record AEs, concomitant treatments, bleeding episodes (including location and etiology – traumatic or spontaneous) and any hemostatic treatments (including intravenous treatments with factor VII products, factor IX products or bypass agents). Hemostatic therapy that is administered to treat bleeding episodes during the Screening period and during the study through the final study visit will be documented as concomitant treatment. Subject diary review will include any bleeding episodes treated with hemostatic agents. Bleeding episodes requiring treatment with intravenous coagulation factor products or bypass agents will count toward the determination of bleeding episode frequency during the period of treatment with PF-06741086. Subject assessment(s) will be captured on the subject diary and reviewed by the investigator at study visits. One assessment per infusion will be required.

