3.2. Secondary Endpoints

3.2.1. Efficacy

- *Annualized rate of bleeding episodes; Day 1 up to Day 85.*

Baseline will be defined as the annualized bleeding rate during the 6 months prior to study enrollment.

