4. ANALYSIS SETS

4.1. Full Analysis Set

In general, the full analysis set is comprised of all enrolled subjects. This population of subjects is not applicable for this study. Analysis sets for efficacy, PK, pharmacodynamic and safety data are defined in [Section 4.3](#), [Section 4.4](#), [Section 4.5](#) and [Section 4.2](#).

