4.3. Per Protocol Analysis Set

The Per Protocol Analysis Set (PPAS) will be a subset of the Safety Analysis Set. This set will exclude subjects with major protocol deviations.

Major protocol deviations include but not limited to:

- Lack of compliance in study drug administration;
- Violations on concomitant medications, see Protocol Section 5.7.1.

The full list of protocol deviations will be reviewed prior to database lock and a decision will be taken regarding exclusion from the PPAS.

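### The ABR comparison is planned only in a per-protocol set that can drop a subject because of how his bleed was treated; no all-treated run is planned

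*SAP*

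**What the plan says.** SAP 6.2.1.1 places the ABR model in the Per Protocol Analysis Set (PPAS): "The efficacy analysis will be conducted in the PPAS". SAP 4.1 says of the full analysis set "This population of subjects is not applicable for this study" and refers efficacy data to Section 4.3. The Safety Analysis Set (SAP 4.2, at least one dose) is assigned to safety analyses and listings.

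SAP 4.3 removes major deviators. It gives two examples in a list that it calls non-exhaustive: non-compliance with study drug, and "Violations on concomitant medications, see Protocol Section 5.7.1". The decision is taken on review before database lock. SAP 4.3 words exclusion as definite, while SAP 4.8 words it as optional.

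Protocol 5.7.1 states "Treatment with APCC (eg, FEIBA) is prohibited throughout the study", and also bars rFVIIa above approximately 90 µg/kg, antifibrinolytics and drugs affecting platelets. After APCC: "Subjects who are treated with investigational product who are subsequently administered APCC therapy must be withdrawn from treatment with investigational product immediately".

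On the endpoint, Protocol 7.2.1 says that bleeds needing intravenous factor "products or bypass agents will count toward the determination of bleeding episode frequency during the period of treatment with PF-06741086". SAP 3.2.1 defines the endpoint as "Annualized rate of bleeding episodes; Day 1 up to Day 85".

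SAP 5.1 calls a dose superior if the estimated ABR ratio to the historical on-demand group is at most 0.3 and its upper 80% limit is below 1.

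**The concern.** Exclusion from the efficacy set can follow from the outcome. A subject who bleeds more has more occasions to receive a prohibited haemostatic treatment. Once he does, he can be removed together with all his bleeds. In a cohort of six, one removal is a sixth of the data.

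The study is open-label, the sponsor included, and SAP 7 has the team reviewing efficacy data routinely. Fixing exclusions before database lock therefore does not mean fixing them without knowledge of the bleed counts.

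The historical group is filtered on age and factor activity, with no stated filter on concomitant treatment. It may be trimmed of very high ABR values, which works against the drug.

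What is at stake is a weaker dose being called superior, with no planned run in all treated subjects to show whether the call depends on who was excluded. The disposition summary (SAP 6.4.2) and the individual ABR listing (SAP 6.5.7.1) would reveal exclusions, but neither recalculates the ratio, the interval or the rule.

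**Working it through.** **Plan's own figure.** Protocol 9.1 claims more than 80% power with 6 subjects per cohort, ratio 0.15, one-sided alpha 0.1, control rate 2.36 bleeds per patient-month and 3 months. Expected treated bleeds are 6 × 3 × 2.36 × 0.15 = 6.37. With an assumed 6 controls, control bleeds are 6 × 3 × 2.36 = 42.48. Then SE = √(1/6.37 + 1/42.48) = 0.425, |ln 0.15|/SE = 1.897/0.425 = 4.47, and power = Φ(4.47 − 1.28) = 99.9%. The claim holds as a lower bound. Lost power is not the problem.

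**How few bleeds decide the rule.** At the design rate a control has 2.36 × 3 = 7.08 bleeds in 3 months. Six treated subjects meet the 0.3 limit only with at most 0.3 × 7.08 × 6 = 12.7, that is 12 bleeds in total.

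Take counts 1, 1, 1, 1, 1, 9:
- All six: (14/6)/7.08 = 0.33, so the rule is not met.
- Without the 9-bleed subject: (5/5)/7.08 = 0.14. With dispersion 1 and 60 controls followed for 6 months (14.16 bleeds each), SE = √[(1/1 + 1)/5 + (1/14.16 + 1)/60] = 0.646. The upper 80% limit is 0.14 × exp(1.28 × 0.646) = 0.32, so both parts of the rule are met.

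**Simulation.**
- From the documents: 6 treated subjects, Day 1 to Day 85 (84 days), 2.36 bleeds per month, and the SAP 5.1 rule.
- Assumed, because the documents do not give them: 60 controls × 6 months; negative binomial dispersion k = 0.5 to 1, treated as known; number of subjects at risk; chance q per bleed of an excluding treatment.
- A subject at risk is excluded with probability 1 − (1 − q)^bleeds.
- SE = √[(1/m_t + k)/n + (1/m_c + k)/60], where m_t and m_c are mean counts per subject. A cohort with no bleeds counts as meeting the rule. There were 200,000 trials per setting.

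Chance of meeting the rule (range over k):

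| Analysis | True ratio 0.15 | 0.50 | 1.0 |
|---|---|---|---|
| All six | 93–95% | 13–20% | 0.3–2.1% |
| 1 of 6 at risk, q = 10% | – | 15–23% | – |
| 2 of 6 at risk, q = 10% | 94–96% | 18–27% | 1.0–4.7% |
| 2 of 6 at risk, q = 5% to 20% | – | 16–30% | – |
| 6 of 6 at risk, q = 10% | – | 34–48% | – |
| Heaviest bleeder always removed (worst case) | – | 36–48% | 2.6–11% |

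**Robustness.** Using 30 or 120 controls moves the all-six, 2-of-6 and worst-case figures by about one point or less. Estimating the dispersion (1,500 trials) gives, at 0.50, 14–19% (all six), 19–26% (2 of 6) and 38–48% (worst case).

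**Opposing step.** Trimming the top 3 of 60 controls lowers the control rate by 10–16%. The 2-of-6 figure at 0.50 then falls to 13–19%. The net direction depends on both discretionary steps.

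**Selection or just a smaller cohort?** Always dropping one random subject at 0.50 gives 16–23%, a rise of about 3 points. In the 1-of-6 setting, however, exclusion is not certain. With a mean of 2.36 × 0.50 × 2.76 months = 3.26 bleeds, its probability is 1 − (1 + k × 3.26 × 0.1)^(−1/k), which is 26% for k = 0.5 and 25% for k = 1. Random removal at that frequency would add about 0.25 × 3 = 0.7 points, against the 2–3 seen. Most of the rise is selection on bleeding.

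**The case against.** The strongest reply is that the route is narrow. Usual factor products and rFVIIa at about 90 µg/kg are permitted for bleeds (Protocol 5.7.2, 7.2.5). Subjects who cannot replace APCC are not enrolled (Protocol 4.2). Protocol 5.7 makes an exception for treating acute bleeds, and for higher-dose rFVIIa Protocol 5.7.1 refers the case to the medical monitor instead of requiring withdrawal. Protocol 3.1 admits inhibitor subjects only at a dose already assessed in subjects without inhibitors, so the first six at a new dose should not be exposed to the bypass-agent route. Efficacy is a secondary endpoint in a Phase 1b/2 safety study. Deviations in other subjects could remove low bleeders.

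Much of this stands as a limit on size. It does not remove the problem:
- The Protocol 5.7 exception defers to 5.7.1, which still bars APCC throughout. The SAP does not say how such use is classified.
- SAP 2.2 lets inhibitor subjects join whichever cohorts are open, which conflicts with Protocol 3.1. The two need reconciling, and the mix per cohort is unknown.
- A bleed treated only with an antifibrinolytic is not an endpoint event. A factor-treated bleed with an antifibrinolytic or a platelet-active drug added is, and it can occur in a subject without inhibitors.
- A study-drug pause after a bleed is allowed ("Pausing or withdrawal of treatment with investigational product is not required in the event of a breakthrough bleed, but may be considered"). Counting it as non-compliance would be a stretch, but nothing in SAP 4.3 rules it out.
- The Protocol Summary plans no formal hypothesis test, but SAP 5.1 sets a superiority rule with hierarchical testing.

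The descriptive ABR tables and the Wilcoxon test (SAP 6.2.1.2, 6.2.1.3) name no analysis set. That they default to the PPAS is a reading of SAP 4.1, not an express statement.

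**Conclusion.** The concern holds. The texts together allow one bleed to be both an endpoint event and the ground for removing the subject, by a discretionary decision in a sponsor-open study, with no all-treated model to compare against.

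At the planned effect the consequence is about one point. At a true ratio of 0.50, the chance of a superiority call rises by 2–3 points with one of six at risk and by 5–7 points with two of six, at 10% per bleed. The rise is larger if a whole cohort is at risk. The worst case is a bound, since no section prescribes removing the heaviest bleeder.

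These sizes depend on the assumed exclusion rate, dispersion and number of controls. The direction is not certain, because trimming the controls pulls the other way. The gap in the plan itself does not depend on those assumptions.

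**What to change.** In SAP 6.2.1.1, run the main ABR model, the 5.1 rule and the 6.2.1.3 Wilcoxon test in the Safety Analysis Set. Count bleeds from Day 1 to Day 85, with each subject's observed time as the offset. Keep the PPAS as supportive. State in 4.3 that how a bleed was treated does not by itself remove a subject from the efficacy analysis.

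Add a supportive run that ends each subject's count and time when study drug stops, keeping the bleed that led to stopping. State this handling explicitly: Protocol 7.2.1 refers to the period of treatment, SAP 3.2.1 to Day 1 to Day 85, and the two differ for anyone withdrawn from drug after APCC.

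The cost is SAP wording, two extra model runs and some dilution from off-drug time. The dilution was simulated with 30,000 trials per setting, two of six at risk, q = 10%, drug stopped at the first prohibited treatment and effect lost at once (pessimistic). A true ratio of 0.15 is then estimated at 0.17–0.18, and the rule is met 87–90% of the time instead of 93–95%. The run ending at drug stop recovers 0.15 and 92–95%. At a true ratio of 0.50 the two runs meet the rule 12–19% and 13–21% of the time, close to the 13–20% with no exclusions.

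Which of these two runs carries the rule is an estimand choice that the sponsor should state. An all-treated run is needed either way.

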##### **4.1. Inclusion Criteria**

Subject eligibility should be reviewed and documented by an appropriate member of the investigator's study team before subjects are included in the study.

Subjects must meet all of the following inclusion criteria to be eligible for enrollment in the study:

1. Evidence of a personally signed and dated informed consent document indicating that the subject (or a legally acceptable representative/parent(s)/legal guardian) has been informed of all pertinent aspects of the study.
2. Males  $\geq 18$  and  $< 65$  years of age.
3. Body Mass Index (BMI)  $\geq 17.5$  and  $\leq 30.5$  kg/m^2 and total body weight  $\geq 50$  and  $\leq 100$  kg.
4. Diagnosis of severe hemophilia A or B (Factor VIII or Factor IX activity  $\leq 1\%$ ).
5. Subjects enrolled as Factor VIII or Factor IX inhibitor patients must have a positive inhibitor test result (above the upper limit of normal) at the local laboratory and must receive a bypass agent as primary treatment for bleeding episodes. A positive inhibitor test result will be above the upper limit of normal for the assay. Inhibitor test results from up to 6 months prior to Day 1 may be used to meet this requirement.
6. Patients with an episodic (on-demand) treatment regimen prior to Screening, who are willing and able to washout from Factor VIII (for at least 72 hours) or Factor IX (for at least 96 hours) replacement therapy, or bypass agent therapy (for rFVIIa and APCC: at least 72 hours), prior to Screening laboratory assessments of factor activity and have no plans to institute prophylactic factor treatment during the study period.

7. Had at least 6 acute bleeding episodes (spontaneous/traumatic) during the 6-month period prior to Screening. Surgical bleeding episodes do not apply to this criterion.
8. If receiving therapy for human immunodeficiency virus (HIV) or active hepatitis infection, have stable disease and be on a stable regimen at the time of study entry (ie, stable dosing for at least 3 months before consent).
9. Willing and able to comply with scheduled visits, treatment plan, laboratory tests, and other study procedures.
10. If with partners currently pregnant or if able to father children, agree to use a highly effective method of contraception throughout the study and for least 28 days after the last dose of investigational product.

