### **9.1. Sample Size Determination**

The total sample size of approximately 24 subjects for 4 dose cohorts is based on clinical considerations to provide adequate safety, tolerability, PK, PD and efficacy information at each dose level and/or route of administration. Each single dose cohort includes 6 subjects to ensure sufficient sample size for assessment of safety, PK, PD and efficacy. Additional subjects and/or cohorts may be added to fully explore the dose range and efficacy.

This sample size is also considered sufficient to support initial analyses for efficacy based on the endpoint of annualized bleeding rate (ABR). With 6 subjects per cohort, there is greater than 80% power to detect an 85% reduction in ABR compared to a historical factor-replacement treatment (control group) at one-sided alpha of 0.1. The power calculation is based on a Poisson regression model with assumptions that the historical control group has a bleeding rate of 2.36/patient-month and the study duration is 3 months.

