5.1. Hypotheses and Decision Rules

Prophylactic treatment with PF-06741086 will be considered superior to On Demand treatment with respect to ABR reduction if 1) the upper limit of the 2-sided 80%CI of the ratio of ABR in PF/historical On Demand is <1 and 2) the estimate of the ratio of ABR in PF/historical On Demand ≤ 0.3 . Drug will be considered not superior to On Demand treatment if the lower limit of the 2-sided 80%CI of the ratio of PF/historical On Demand >0.3 .

The primary efficacy endpoint in the four dose cohorts will be tested in a hierarchical order to control the overall family-wise error rate. The efficacy test will first be performed in the dose cohort with the highest PK exposure (eg, C_{trough} and/or AUC) that is proven to be safe and tolerated. If the result is significant, the ABR will be tested against the historical On Demand group in the dose cohort with the next highest PK exposure. The test procedure will continue until the dose cohort with the lowest PK exposure is tested against the historical On Demand group.

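### The historical On Demand control is not matched or adjusted for prior bleeding frequency, although B7841002 selects its subjects on it, so the ABR ratio is confounded in a direction the documents do not settle

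*SAP*

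**What the plan says.** Protocol 4.1, criterion 7, requires that a subject "Had at least 6 acute bleeding episodes (spontaneous/traumatic) during the 6-month period prior to Screening"; surgical bleeds do not count. The Protocol Summary and Section 3 repeat this history in their short descriptions of the population, next to factor activity and the on-demand regimen.

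SAP 6.2.1.1 builds the control from on-demand data in three internal studies (B1831004, B1821010, B1821004). It filters the pool to "match the key inclusion/exclusion criteria of B7841002 based on age and factor activity" and names no other matching variable. It adds that "Outliers with extremely high ABR will be removed from the pooled On Demand group, if appropriate", without a rule for what counts as extreme.

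SAP 5.2.3 fits a negative binomial model with treatment as the only term and log time as offset. SAP 3.2.1 defines the pre-study ABR as baseline, but SAP 6.2.1.2 only summarises and plots it. The Wilcoxon test in SAP 6.2.1.3 is planned against the same historical group.

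SAP 5.1 declares superiority if "the upper limit of the 2-sided 80%CI of the ratio of ABR in PF/historical On Demand is <1" and "the estimate of the ratio of ABR in PF/historical On Demand ≤ 0.3".

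**The concern.** Of the entry criteria, number 7 is the one that selects on the outcome itself. If bleeding tendency persists within a subject, people chosen for a high recent count have a higher expected untreated rate than the population they came from. Under this plan that selection is certain on the treated side and unspecified on the control side. Nothing downstream repairs it, because the model does not adjust for prior bleeding and the sensitivity analysis reuses the same control.

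Protocol 1.3.2 names this external comparison as the measure of therapeutic efficacy. One part of the success rule is a fixed cut-off of 0.3 on the point estimate, so a modest multiplicative bias matters for any dose whose true ratio lies near 0.3.

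**Working it through.** **Inputs from the documents.** Planned control: "historical control group has a bleeding rate of 2.36/patient-month and the study duration is 3 months" (Protocol 9.1). This is 2.36 × 12 = 28.3 bleeds/year, or 14.16 per 6 months. The entry floor is 6 per 6 months, or 12/year. There are 6 subjects per cohort, the planned ratio is 1 − 0.85 = 0.15, and alpha is 0.1 one-sided.

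**The plan's own figure.** Protocol 9.1 says "With 6 subjects per cohort, there is greater than 80% power to detect an 85% reduction in ABR". I used a Wald test on the log rate ratio under Poisson. The expected count per control subject is 2.36 × 3 = 7.08, and per treated subject 0.15 × 7.08 = 1.062. With 6 controls, SE² = 1/(6 × 1.062) + 1/(6 × 7.08) = 0.1805, so SE = 0.425. Power = Φ(1.897/0.425 − 1.2816) = 99.9%. The statement is correct as a lower bound.

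**Effect of the entry criterion taken alone.** Assumptions, none of them in the documents:
- trial subjects and controls come from one population with mean 28.3/year;
- annual rates vary between subjects as a gamma distribution with shape a;
- 6-month counts N are Poisson given the rate;
- the source studies had no bleed entry rule.

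With b = a/28.32, the expected annual rate given entry is (a + E[N | N ≥ 6]) / (b + 0.5). Dividing by 28.32 gives the factor by which the ratio is inflated.

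For a = 1, N is geometric, so E[N | N ≥ 6] = 6 + 14.16 = 20.16. The expected rate is (1 + 20.16)/(0.0353 + 0.5) = 39.5/year, and the factor is 39.5/28.3 = 1.40.

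| Shape a | Controls failing criterion 7 | E[N given N ≥ 6] | Rate given entry (/year) | Factor | True 0.15 reads | True 0.25 reads | True ratio that reads 0.30 |
|---|---|---|---|---|---|---|---|
| 5 | 9% | 15.2 | 29.9 | 1.05 | 0.16 | 0.26 | 0.28 |
| 2 | 21% | 17.1 | 33.5 | 1.18 | 0.18 | 0.30 | 0.25 |
| 1 | 34% | 20.2 | 39.5 | 1.40 | 0.21 | 0.35 | 0.21 |

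**Can the net effect go the other way?** Yes. The break-even is an untreated trial rate equal to the control rate, 28.3/year on the planning figure. Criterion 7 guarantees only a recent count equivalent to 12/year. If the trial's source population averaged 1.5 bleeds/month (18/year), the same calculation after selection gives factors of 0.68 to 0.85 for shapes 10 to 2. At 1.0/month it gives 0.49 to 0.79 for shapes 10 to 1. A factor of 0.65 would let a true ratio of 0.30/0.65 = 0.46 read 0.30, in the drug's favour.

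**Effect on the two-part rule.** Assume 50 controls and dispersion 0.5 (shape 2). Let q be the true ratio times the factor. Then SE² = (1/(7.08q) + 0.5)/6 + (1/7.08 + 0.5)/50. In every cell below the 0.3 cut-off is the binding part, so the chance of success is Φ(ln(0.3/q)/SE).

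| True ratio | Factor 0.6 | Factor 1 | Factor 1.25 |
|---|---|---|---|
| 0.15 | 98% | 92% | 84% |
| 0.30 | 86% | 50% | 29% |

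**The case against.** The strongest reply is that the sign is not established. A reader might infer from criterion 7 that the whole comparison is biased against the drug. That needs a control pool unselected on bleeding and drawn from the same population as the trial. The documents give neither. If the source studies had a similar entry rule, the mismatch largely disappears. If untreated trial subjects bleed at less than the control rate, the ratio favours the drug. This stands, and it limits the claim to the contribution of the missing criterion. It does not remove the problem: a ratio confounded in an unknown direction still cannot be read against 0.3 with confidence.

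A reader might also infer that an effective dose would be declared a failure. At the planned effect the largest factor above gives 0.21, well inside 0.3. A true ratio of 0.25 still meets the cut-off at shapes 5 and 2. Nor is bias the main cause of near misses: with 50 controls and dispersion 0.5, an unbiased true ratio of 0.25 misses about 34% of the time, and 0.30 misses half the time.

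A third tempting inference is that missing 0.3 stops testing in the remaining cohorts. SAP 5.1 makes the next test depend on a significant result and does not say whether that means both parts of the rule. SAP 6.2.1.3 attaches significance to a one-sided p-value below 0.1. So the stop follows on one reading only.

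Lastly, ABR is a secondary endpoint, the Protocol Summary says no formal hypothesis is planned, and pre-study ABR is plotted beside on-study and historical ABR. An imbalance might therefore be noticed. It would still not be adjusted for, and SAP 5.1 does set a formal decision rule.

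**Conclusion.** The mismatch is real: the plan says it matches on key criteria but omits the one most closely tied to the outcome, and neither the model nor the sensitivity analysis compensates. Taken alone, the omission inflates the ratio by 1.05 to 1.40, given a common population with mean 28.3/year, gamma shape 5 to 1 and no bleed entry rule in the source studies. Undefined removal of high-ABR controls would push the same way, since it too lowers the control rate.

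The net direction and size cannot be determined from the documents. The consequence is material for true ratios near 0.3 and small at the planned 0.15. For a key secondary objective in a Phase 1b/2 study this should be corrected, but it does not invalidate the design.

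**What to change.** In SAP 6.2.1.1:

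1. State the bleed entry criteria of the three source studies.
2. Add criterion 7 to the control filter: at least 6 non-surgical bleeds in the 6 months before the source study, or an equivalent rate. Use recorded pre-study history and not the on-demand period being analysed, because selecting on the analysed period would itself inflate the control rate.
3. Report the ratio with and without the filter, and with and without any source study that lacks this history.
4. Set the filter without reference to accumulating ABR results, and date it. Protocol 9.7 and SAP 7 have the study team routinely reviewing efficacy data in this open study, and the filter may favour the drug. The unfiltered ratio should therefore stay visible.
5. Fix the rule for removing high-ABR controls in advance, since it acts on the same control rate.

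The cost is SAP wording and a filter on the sponsor's own data. The downsides are a smaller control group and dependence on pre-study bleed counts having been recorded, which the documents do not confirm. The filter also cannot correct for a difference between the source populations, which is another reason to show both ratios.
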